Baseline period	Baseline	From ediary device assignment date (or week -4 visit)	Day prior to study day 1
Treatment Period	Week 4	Study day 1	
• Week 4 visit date - 1• Study day 1 + 27 days if Week 4 visit is missed 
Note: if day 1 dose is the last dose subject received, the rest of monthly rates during treatment period will be calculated based on consecutive 28-day interval beginning

	Week 8	
• Week 4 visit date• Week 4 analysis visit end date + 1 day if Week 4 visit is missed	
• Week 8 visit date – 1• Week 4 analysis visit start date + 27 days if Week 8 visit is missed
	Week 12	
• Week 8 visit date• Week 8 analysis visit end date + 1 day if Week 8 visit is missed	
• Week 12 visit date – 1• Week 12 analysis visit start date + 27 days if Week 12 visit is missed
	Week 16	
• Week 12 visit date	
• Week 16 visit date – 1

		
 • Week 12 analysis visit end date + 1 day if Week 12 visit is missed 	
 • Week 16 analysis visit start date + 27 days if Week 16 visit is missed
	Week 20	
 • Week 16 visit date • Week 16 analysis visit end date + 1 day if Week 16 visit is missed 	
 • Week 20 visit date – 1 • Week 20 analysis visit start date + 27 days if Week 20 visit is missed
	Week 24	
 • Week 20 visit date • Week 20 analysis visit end date + 1 day if Week 20 visit is missed 	
 • Week 24 visit date – 1 • Week 24 analysis visit start date + 27 days if Week 24 visit is missed
	Week 28	
 • Week 24 visit date • Week 24 analysis visit end date + 1 day if Week 24 visit is missed 	
 • Week 28 visit date – 1 • Week 28 analysis visit start date + 27 days if Week 28 visit is missed
	Week 32	
 • Week 28 visit date • Week 28 analysis visit end date + 1 day if Week 28 visit is missed 	
 • Week 32 visit date – 1 • Week 32 analysis visit start date + 27 days if Week 32 visit is missed

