5.1.4 Other imputations

5.1.4.1 eDiary data

The eDiary includes the following clinical outcome assessments:

- Incidence of headache (ie, migraine with or without aura or non-migraine headache)
- Time of onset of headache
- Time of resolution of headache
- Pain severity per headache

- Symptoms (eg, nausea, vomiting, photophobia, phonophobia)
- Presence of aura
- Use of acute medication during aura or to treat headache

as well as, patient-reported outcomes (PROs) measures.

Missing eDiary data in the calculation of monthly measurements about subjects' migraine and non-migraine headaches will be handled using the following method:

1. For monthly intervals with ≥ 14 days of eDiary days (including retrospective eDiary days) in each interval:

a) Monthly frequency measurements (including migraine days, headache days, migraine attacks, [REDACTED]) will be prorated to 28-day equivalents. Prorated result does not need to be rounded.

[REDACTED]

2. For monthly intervals with < 14 days of eDiary use (including retrospective eDiary days), all monthly measurement will be set as missing and will be handled as described in [Section 5.1.5.3](#).

Table 5-2 Rules for handling missing and incomplete eDiary data

Monthly Endpoint	Condition	Proration Method (does not need to be rounded)
Monthly frequency measurements (including migraine days, headache days, migraine attacks, hours of migraine headaches, [REDACTED] [REDACTED])	If diary days in entire baseline or interval post baseline ≥ 14 (including retrospective eDiary days), then do proration; Else monthly measurement is set to missing [diary days is a day with all headache related questions completed retrospectively or not]	Number of observed migraine days * 28/ Number of information days in interval [information day is a diary day or headache day]

Missing PROs scheduled to be collected at office visit at certain assessment will not be imputed.

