If the subject took a migraine-specific medication (ie, triptan or ergotamine) during aura, or to treat a headache on a calendar day, then it will be counted as a migraine day regardless of the duration and pain features/associated symptoms.
 - Monthly Migraine Days

Number of migraine days between each analysis visit that are normalized in a 28-day interval. Monthly migraine days at baseline are the number of migraine days in the baseline period that are normalized in a 28-day interval. Days without eDiary data in each normalized monthly interval will be prorated. All details of calculation are in [Section 5.1.4](#) (The same proration method will be applied for other efficacy endpoints thereafter).

- Duration of Migraine

The duration of migraine in years (migraine with aura or migraine without aura, whichever is earlier) is calculated by the following formula: current age (in years) - age at migraine onset (in years).

Current age is calculated by the following formula, the date of informed consent – birth date (at least the year).

If the current age calculated as detailed above or the age at migraine onset is missing then duration of migraine will be missing.

- Achievement of at least a 50% reduction from baseline in monthly migraine days at month 12

Calculated based on the following: if (monthly migraine days in the last month of the treatment period - baseline monthly migraine days)*100/baseline monthly migraine days is less than or equal to - 50%

- Migraine Attack

An episode of any qualified migraine headache or migraine specific medication intakes for aura only. The following rules will be used to distinguish an attack of long duration from two attacks, or to distinguish between attacks and relapses:

a) A migraine attack that is interrupted by sleep, or temporarily remits, and then recurs within 48 hours will be considered as one attack and not two.

b) An attack treated successfully with medication but with relapse within 48 hours will be considered as one attack.

c) A migraine attack lasting more than 48 hours will be counted as one attack.

- Monthly Migraine Attacks

Number of migraine attacks between each analysis visit. Monthly migraine attacks at baseline are the number of migraine attacks in baseline period. Days without eDiary data are handled by proration according to [Section 5.1.4](#).

[figure not shown]
[figure not shown]
[figure not shown]
[figure not shown]
[figure not shown]
[figure not shown]
[figure not shown]

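### SAP 2.1.1.6 has two low-impact window errors: a missed Week 8 visit loses the Week 8 migraine-day value and can stretch Week 12 over two months, and Days 199–211 are mapped to Week 32 against the table's own rule

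*SAP*

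**What the plan says.** SAP 2.1.1.6 holds two separate window tables.

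**Table 2-3 (eDiary intervals for monthly efficacy values).** The Week 4 interval starts on Study Day 1 and ends the day before the Week 4 visit, or at "Study day 1 + 27 days if Week 4 visit is missed". The Week 8 interval starts on the Week 4 visit date, or the day after the Week 4 interval ends if that visit was missed. If the Week 8 visit is missed, it ends at "Week 4 analysis visit start date + 27 days if Week 8 visit is missed". Week 12 then starts at "Week 8 analysis visit end date + 1 day if Week 8 visit is missed". The Week 12 row uses a different pattern for its own end date: "Week 12 analysis visit start date + 27 days if Week 12 visit is missed". The rows for Weeks 16 to 48 follow that Week 12 pattern. A note exempts a subject "if day 1 dose is the last dose subject received" and gives that subject consecutive 28-day intervals.

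Two rules elsewhere act on these intervals. SAP 5.1.4.1 says: "For monthly intervals with < 14 days of eDiary use (including retrospective eDiary days), all monthly measurement will be set as missing". Intervals with at least 14 diary days "will be prorated to 28-day equivalents". SAP 5.6 defines MMD accordingly: "Number of migraine days between each analysis visit that are normalized in a 28-day interval".

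**Table 2-1 (windows for laboratory, vital signs, C-SSRS and office-visit PROs).** The footnote sets each window from 12 days before to 15 days after the target day. The printed windows are Days 184–198 for Week 28 (target 196) and Days 199–239 for Week 32 (target 224).

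**The concern.** The Week 8 end date is anchored one interval too early. Followed literally, a subject who misses the Week 8 visit but fills in the diary every day loses the Week 8 value. The lost days then move into the next interval, where they are labelled Week 12. For a late Week 4 visit the Week 8 end date even precedes its start date.

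At stake are the Week 8 and Week 12 MMD values, the early points of the secondary cumulative-average analysis (SAP 2.7.2 tabulates estimates and nominal p-values by visit, and SAP 2.7.3 does not impute MMD), and the Week 8 and Week 12 inputs to the multiple imputation in SAP 5.1.4.3.2.

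In Table 2-1, an in-window but slightly late Week 28 assessment is labelled Week 32, which leaves Week 28 blank.

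**Working it through.** **Part (a), Table 2-3.** Inputs: Study Day 1 = 1; visits otherwise on target (Week 4 on Day 28, Week 8 on Day 56, Week 12 on Day 84); minimum 14 diary days; values scaled to 28 days.

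1. *All visits attended.* Week 8 = Day 28 to 56 − 1 = Days 28–55. Week 12 = Days 56–83. Each has 28 days, as intended.
2. *Week 8 missed, as written.* Week 8 end = 1 + 27 = Day 28. With the Week 4 visit on Day d, length = max(0, 29 − d):

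| Week 4 visit | Week 8 days |
|---|---|
| Day 16 | 13 |
| Day 23 | 6 |
| Day 28 | 1 |
| Day 29 or later | 0 |
| missed (start Day 29) | 0 |

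All are below 14, so Week 8 is missing. Only a Week 4 visit before Day 16, the start of the Table 2-1 Week 4 window, would reach 14 days.

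3. *Week 12, as written.* Start = 28 + 1 = Day 29; end = 84 − 1 = Day 83; length 55 days, scaled to 28. Counts are not doubled, but the value is a two-month rate. If Week 12 is also missed, Week 12 takes Days 29–56 and Week 16 becomes Days 57–111 (55 days). For a Week 4 visit on Day 33, Days 29–32 fall in both Week 4 and Week 12.
4. *Week 8 end set to its own start + 27.* Week 8 = Days 28–55; Week 12 = Days 56–83.

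*Size in one affected subject.* The documents give no monthly trajectory. **Assumed** changes from baseline are −2 (month 1), −3 (month 2) and −3.5 afterwards.

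- Week 12 value: (27 × −3 + 28 × −3.5)/55 = −3.25 as written, −3.50 corrected.
- The cumulative average depends on its derivation. Protocol 12.5.1 and SAP 2.7.2 describe averaging monthly values; SAP 5.6 pools diary days.
- *Averaging the available monthly values* (a convention assumed here):
  - Week 8: −2.00 versus (−2 − 3)/2 = −2.50.
  - Week 12: (−2 − 3.2545)/2 = −2.63 versus (−2 − 3 − 3.5)/3 = −2.83.
  - Month 12: (−2 − 3.2545 − 35)/12 = −3.354 versus (−2 − 3 − 38.5)/13 = −3.346.
- *Pooling diary days over the Table 2-3 intervals*:
  - Week 8: (27 × −2 + 1 × −3)/28 = −2.04 versus (27 × −2 + 28 × −3)/55 = −2.51.
  - Week 12: −236/83 = −2.843 both ways.
  - Month 12: −1216/363 = −3.350 both ways.
  - With the Week 4 visit on Day 33, if the overlapping days are counted twice: Week 12 is −248/87 = −2.851 versus −2.843, and month 12 is −1228/367 = −3.346 versus −3.350.

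Shift (as written minus corrected) with visits on target, over **assumed** changes of −1 to −3 (month 1), −2 to −4 (month 2) and −3 to −5 (later):

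| Quantity | Averaged | Pooled |
|---|---|---|
| Week 8 cumulative | −0.50 to +1.50 | −0.47 to +1.42 |
| Week 12 cumulative | −0.09 to +0.58 | 0 |
| Month 12 cumulative | −0.095 to +0.049 | 0 |

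The Week 12 monthly value itself shifts by (27/55) × (month 2 − later), that is −0.49 to +1.47.

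*Primary endpoint.* The Week 52 interval is anchored on the Week 48 visit and stays at Days 336–363. It moves (to Days 309–336) only if all visits from Week 8 to Week 48 are missed.

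**Part (b), Table 2-1.** Applying target − 12 to target + 15 reproduces 11 of the 13 printed rows. The other two:

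| Visit | Printed | By the rule |
|---|---|---|
| Week 28 (target 196) | 184–198 (15 days) | 196 − 12 to 196 + 15 = 184–211 |
| Week 32 (target 224) | 199–239 (41 days) | 224 − 12 to 224 + 15 = 212–239 |

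Days 199–211 (13 days) are misassigned. Of these, Days 199–201 are 3 to 5 days after the Week 28 target and so inside the +5-day visit window of protocol section 8. Day 199 is 3 days from the Week 28 target and 25 from the Week 32 target.

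**The case against.** The strongest reply on Table 2-3 is that the Week 8 cell is only loosely worded. If it means the date of the Week 4 visit, then adding 27 gives Days 28–55, the right interval, and the Week 52 row does count from the previous visit date. That reading does not fit the table. The rows for Weeks 12 to 48 use the same term for the start of an interval, and the Week 4 interval starts on Study Day 1. It also gives no date when the Week 4 visit was missed too. It may be what was intended, but it is not what the cell says.

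On Table 2-1, the governing rule is printed directly underneath, so a careful programmer would notice the conflict. Usually a misassigned record loses to one nearer Day 224, so the effect is one fewer Week 28 value; a wrong Week 32 value arises only when Week 32 has no closer record. That stands as a limit on impact, but it does not settle which of the two statements is to be programmed.

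Several other limits also stand. The shifts are per affected subject and rest on assumed trajectories; the group effect scales with the unknown fraction who miss Week 8. Remote or home contacts during COVID-19 may count as visits, which narrows the trigger. SAP 2.7.2 describes the Week 8 cumulative value as using data from Weeks 1 to 8, so it need not pass through the faulty interval. The route to the primary endpoint is nearly empty, because a subject who misses all those visits would rarely count as a treatment completer.

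**Conclusion.** Both errors hold as written, and both are low impact.

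(a) Except for subjects whose Day 1 dose was their last, a missed Week 8 visit makes Week 8 MMD missing for any Week 4 visit on Days 16–43 or a missed one. It also turns Week 12 into a two-month average (55 days on target visits) when the Week 12 visit is attended. The month-12 cumulative average, for which SAP 5.5.2 states the hypothesis, moves by at most about 0.1 day per affected subject over the assumed range. It does not move if distinct diary days are pooled. The imputation inputs matter only for sensitivity and supplementary analyses; for the primary endpoint, SAP 2.5.4 limits imputation to treatment completers with missing Week 52 MMD. The rule is the same in both arms, and no bias in the treatment contrast is claimed.

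(b) This mainly affects by-visit vital-sign summaries. Mandatory post-baseline chemistry in the oral-prophylactic arm falls at Weeks 24 and 52 (protocol Table 8-1), and neither the any-visit counts of notable vital signs nor diary MMD use these windows to select a visit.

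The tables should be corrected because literal programming gives wrong by-visit values, and silent correction would depart from a final SAP.

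**What to change.** Change three table cells in SAP 2.1.1.6:

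- Table 2-3, Week 8 end date when the visit is missed: start date of the Week 8 interval plus 27 days, the pattern already used for Weeks 12 to 48.
- Table 2-1, Week 28: Days 184–211.
- Table 2-1, Week 32: Days 212–239.

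Then check the derivation code against both corrected tables before database lock. The cost is three cells and one check of the derived-dataset code; no data collection or clinical procedure changes.

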A copy of the approved version of all consent forms must be provided to Novartis after IRB/IEC approval.

Subjects might be asked to complete an optional questionnaire to provide feedback on their clinical trial experience.

During the COVID-19 pandemic that may challenge the ability to obtain a standard written informed consent due to limits that prevent an on-site visit, the Investigator may conduct the informed consent discussion remotely (e.g. telephone, videoconference). Guidance issued by local regulatory bodies on this aspect prevail and must be implemented and appropriately documented (e.g. the presence of an impartial witness, sign/dating separate ICFs by trial participant and person obtaining informed consent, etc).

During the COVID-19 pandemic the Investigator should discuss the home-delivery of study drug, and should provide detailed step by step instructions for the proper method for self-administration of study drug including: 1) the correct handling, 2) self-administration procedure, and 3) storage of study drug. This training may be done in person or videoconference or by telephone if patient visits to site are not possible. This training process needs to be documented in the patient's source documents with the patient's verbal/e-mail/ or chat function agreement. Guidance issued by local regulatory bodies on this aspect prevail and must be implemented and appropriately documented (e.g. the presence of an impartial witness, sign/dating separate ICFs by trial participant and person obtaining informed consent, etc.). Written informed consent must be obtained once protocol amendment 2 is approved at the site.

8 Visit schedule and assessments

Assessment schedule [Table 8-1](#) and [Table 8-2](#) lists all of the assessments and indicates with an "X" when those assessments are performed. All data obtained from these assessments must be supported in the subject's source documentation.

Visit windows for each visit must be completed within +5 days from Day 1 with visits occurring every 28 days as described in [Table 8-1](#) and [Table 8-2](#). In addition, visits need to be scheduled within the protocol specified visit windows to ensure that drug is administered within dosing windows (23 to 33 days from previous dose).

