Switched treatment period (core phase)	Date of first switch on DS domain	
 1. Subject completes 52 weeks on switched treatment i.e. core phase treatment disposition reason is "COMPLETED" and week 52 visit date is non-missing in SV domain 
 a. If subject does not enter PTA phase then use week 52 visit date from SV domain b. If subject enters PTA phase then 
 i. Subject enters PTA on week 52 visit date then use a day prior to week 52 visit date ii. Subject enters PTA phase after week 52 then use week 52 visit date 2. Subject completes 52 weeks on core phase but discontinues switched treatment early i.e. core phase trt disposition reason is not equal to "COMPLETED" on DS domain 
 a. If subject does not enter PTA phase 
 i. if week 52 visit date $>$ treatment end date plus 27/1 day then use treatment end date plus 27/1 day ii. if week 52 visit date \leq treatment end date plus 27/1 day then use week 52 visit date b. If subject enters PTA phase 
 i. if week 52 visit date $>$ treatment end date plus 27/1 day then use treatment end date plus 27/1 day ii. if week 52 visit date \leq treatment end date plus 27/1 day then use a day prior to first dose in PTA phase 3. Subject does not complete 52 weeks on switched treatment i.e. core phase trt disposition reason is not

		equal to “COMPLETED” on DS domain and week 52 visit date is missing in SV domain then use min(treatment disposition date, treatment end date plus 1 day)
--	--	--

Note: DS: Disposition domain; SV:Visit domain; IAT: Initially assigned treatment

Monthly interval for efficacy endpoints (from ediary)

Monthly efficacy measurements will be calculated based on the subject's starting dose and visit schedule defined below using eDiary data collected from beginning of the baseline phase (week -4 visit) up to week 52 visit if subjects do not have safety follow up visit. For subjects with safety follow up, consider data up to the safety follow-up visit. The algorithm remains the same for initially assigned treatment and switched treatment. ediary data will be collected during core phase only and will not be collected during extension phase.

Table 2-3 Study intervals for efficacy endpoints – Erenumab and Oral prophylactics

Study phase	Assessment Time point	Interval based on dose dates	
		Start date	End date

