	Week 36	
 • Week 32 visit date • Week 32 analysis visit end date + 1 day if Week 32 visit is missed 	
 • Week 36 visit date – 1 • Week 36 analysis visit start date + 27 days if Week 36 visit is missed
	Week 40	
 • Week 36 visit date • Week 36 analysis visit end date + 1 day if Week 36 visit is missed 	
 • Week 40 visit date – 1 • Week 40 analysis visit start date + 27 days if Week 40 visit is missed
	Week 44	
 • Week 40 visit date • Week 40 analysis visit end date + 1 day if Week 40 visit is missed 	
 • Week 44 visit date – 1 • Week 44 analysis visit start date + 27 days if Week 44 visit is missed
	Week 48	
 • Week 44 visit date • Week 44 analysis visit end date + 1 day if Week 44 visit is missed 	
 • Week 48 visit date – 1 • Week 48 analysis visit start date + 27 days if Week 48 visit is missed
	Week 52	
 • Week 48 visit date • Week 48 analysis visit end date + 1 day if Week 48 visit is missed 	
 • MIN (Week 48 visit date + 27, EoS) 
MIN (Week 52 analysis visit start date + 27 days if Week 48 visit is missed, EoS)

Where EoS date is the date of the end of study visit.

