2.5.3 Handling of missing values/censoring/discontinuations

Subjects with missing monthly migraine day data at week 52 of treatment, and subjects that discontinue initially assigned treatment prior to the week 52 visit will be imputed as non-responders (not achieving a net benefit).

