5.6 Important derivations

- Subject-level End of Study (EOS) Date

The end of study (EOS) date for each subject is defined as the last date on which the subject participated in the study. The date will be recorded on the study disposition eCRF page.

- Duration of exposure of study treatment

For AMG334 calculation of exposure, dose date refers to receiving dose > 0 , but can include partial doses. The duration of exposure for AMG334 is computed as of last injection of study drug + 27 days - date of first injection of study drug +1.

For oral prophylactics arm calculation of exposure, dose date refers to receiving dose > 0 . The duration of exposure for initially assigned treatment is computed as last dose date - First Dose Date + 1.

- Compliance with the eDiary

The protocol requirement is 80% compliance in 28 days. That means a minimum 23 diaries must be completed within 28 days. Compliance to eDiary at each month is calculated as

- (Number of eDiary entered in baseline period or between IP doses/28days)*100% if the number of actual days in Baseline period or between IP doses interval is ≤ 28 days
 - (Number of eDiary entered in baseline period or between IP doses/ number of actual days in Baseline period or between IP doses interval)*100% if the number of actual days in Baseline period or between IP doses interval is > 28 days
 - eDiary Device Assignment Date

The date on which an eDiary device is assigned to a subject for the first time after completion of initial screening at week -4 visit.
 - eDiary Day

A day in which a subject uses the eDiary.
 - Information Day

A day which is either a headache day or an eDiary day.
 - Migraine Day

A migraine day is defined as any calendar day in which the subject experiences a qualified migraine headache (onset, continuation, or recurrence of the migraine headache). Please see exceptions in [Appendix 5.7](#). A qualified migraine headache ([IHS, 2013](#)) is defined as a migraine with or without aura, lasting for ≥ 30 minutes, and meeting at least one of the following criteria:

 1. ≥ 2 of the following pain features:
 - Unilateral
 - Throbbing
 - Moderate to severe
 - Exacerbated with exercise/physical activity
 2. ≥ 1 of the following associated symptoms:
 - Nausea and/or vomiting
 - Photophobia and phonophobia

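### The Week 52 diary interval starts at the attended Week 48 visit and cannot reach back, so a far out-of-window Week 48 visit can turn a completer with a recorded last month into a non-responder

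*SAP*

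**What the plan says.** SAP section 2.1.1.6, Table 2-3, builds each diary month from actual visit dates. The Week 52 month starts on the Week 48 visit date and ends at "MIN (Week 48 visit date + 27, EoS". Only if that visit did not take place is the start rebuilt from the preceding interval: "Week 48 analysis visit end date + 1 day if Week 48 visit is missed". The same section uses diary data "up to week 52 visit if subjects do not have safety follow up visit". It adds that data up to the follow-up visit are considered where there is one, and that no diary is collected in the extension.

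Protocol section 8 ties visits to Day 1: "Visit windows for each visit must be completed within +5 days from Day 1 with visits occurring every 28 days". It also says that missed or rescheduled visits should not lead to automatic discontinuation.

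SAP section 5.1.4.1 prorates months with at least 14 diary days to 28 days. For shorter ones: "For monthly intervals with < 14 days of eDiary use (including retrospective eDiary days), all monthly measurement will be set as missing". SAP section 2.5.3 then scores as non-responders "Subjects with missing monthly migraine day data at week 52 of treatment".

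EoS has two meanings. Under Table 2-3: "Where EoS date is the date of the end of study visit". In SAP section 5.6 it is "defined as the last date on which the subject participated in the study".

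**The concern.** Because visits are scheduled from Day 1, a late Week 48 visit does not move Week 52. The delay shortens the last diary month day for day. The days before the late visit are still in the diary, but they are all allocated to the Week 48 month. Once fewer than 14 diary days remain, a subject who stayed on the initially assigned treatment for a year, and may have had a 50% reduction, fails the primary endpoint because of visit timing alone.

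The rule is also uneven. Of two subjects with identical diaries, the one who attends Week 48 very late can be scored worse than the one who does not attend. Nothing in the SAP suggests that this is intended.

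**Working it through.** **Inputs.** Scheduled days are Week 44 = 308, Week 48 = 336 and Week 52 = 364 (Protocol Table 8-1, SAP Table 2-1). The interval rule is in Table 2-3, and the minimum is 14 diary days (SAP section 5.1.4.1).

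**Formula.** Available days n = min(W48 + 27, E) − W48 + 1, where W48 is the Week 48 visit day and E is the last usable diary day. Read literally, E is the Week 52 visit day, 364. If that day carries no usable entry, E = 363; the earlier rows of Table 2-3 all end the day before the next visit.

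| Week 48 visit on day | Days late | n, E = 364 | n, E = 363 |
|---|---|---|---|
| 336 | 0 | 28 | 28 |
| 341 | 5 | 24 | 23 |
| 346 | 10 | 19 | 18 |
| 350 | 14 | 15 | 14 |
| 351 | 15 | 14 | 13 |
| 352 | 16 | 13 | 12 |

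On schedule, the rule gives its intended 28 days. With a full diary it fails at 16 days late (E = 364) or 15 days late (E = 363).

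**Missed Week 48, same diary.** The Week 48 month is days 308 to 308 + 27 = 335. The Week 52 month is days 336 to min(336 + 27, 364) = 363, which is 28 days.

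**Incomplete diary (assumption).** Suppose each day is completed independently with probability c. Then P(missing) = P(Binomial(n, c) ≤ 13).

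| n | c = 0.9 | c = 0.8 |
|---|---|---|
| 24 | <0.1% | 0.4% |
| 23 | <0.1% | 0.9% |
| 19 | 0.9% | 16% |
| 18 | 2.8% | 28% |
| 16 | 21% | 65% |
| 15 | 45% | 83% |

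A Week 48 visit 5 days late leaves n = 23 or 24, so the risk is at most about 1% even at 80% compliance. At 10 days late (n = 18 or 19) it is 16% to 28% at 80% compliance and 1% to 3% at 90%.

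**Which subjects a later EoS protects.** Under SAP section 5.6, EoS can fall well after Week 52. The interval is then nominally 28 days. Without a follow-up visit, however, diary data stop at Week 52, so the diary-day count does not rise. A later EoS helps only if diary entries continue, that is, for subjects with safety follow-up.

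**Scale on the planned figures.** The planned sample size is not in dispute: at 394:197, control rate 0.18 and odds ratio 2, power is 0.900 with continuity correction and 0.917 without. The erenumab rate is 0.3600/1.1800 = 0.305. Expected oral responders are 197 × 0.18 = 35.5. No loss rate is given, so 1% to 5% of responders is purely an assumption:

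- equal loss in both arms: odds ratio 1.996 to 1.979, uncorrected power 0.914 to 0.898;
- oral arm only: 35.5 × 0.01 to 0.05 = 0.4 to 1.8 subjects, odds ratio 2.02 to 2.13;
- erenumab arm only: odds ratio 1.97 to 1.86.

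**The case against.** The best defence is that the plan already contains most cases. Visits inside the stated window leave 23 to 28 days and are prorated. Even if the window is read as ±5 days, the worst pair (Week 48 on day 341, Week 52 on day 359) leaves 19 days by the literal rule. That is enough with a full diary, though less safe with a poor one. This stands: the defect belongs to far out-of-window visits.

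Second, Table 2-1 maps days 324 to 351 to Week 48 and days from 352 to Week 52. A visit 16 days late falls on day 352. If that mapping governed Table 2-3, the visit would no longer count as Week 48 and the missed-visit rule would restore 28 days. But the lead-in to Table 2-1 names laboratory tests, vital signs, C-SSRS and office questionnaires, not the diary, so this is unresolved. It would also not help a subject 10 to 15 days late with an incomplete diary.

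Third, completers with missing Week 52 MMD are multiply imputed under a missing-at-random assumption in a sensitivity analysis (SAP section 2.5.4), and section 5.1.4.3 calls for review of missing data. That is useful, but it leaves the primary result unchanged and imputes a month that may have been recorded.

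A reader might infer a bias favouring erenumab, because an erenumab subject dosed at Week 48 and again on entering the extension at Week 52 is held to 23 to 33 days between doses. The documents do not support that. The visit window covers both arms, not every erenumab subject enters the extension, and Protocol section 6.7.2 foresees doses outside the window after discussion. A reader might also expect the pandemic to make this common. Protocol sections 8 and 8.3 let remote contacts replace site visits and let diary collection continue.

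**Conclusion.** The point holds in a narrow form. For a completer without safety follow-up, with Week 48 far out of window and Week 52 on schedule, Table 2-3 can discard a recorded last month and score non-response, where a missed Week 48 visit would have kept 28 days. With a full diary the threshold is 15 or 16 days late, depending on whether the Week 52 visit day counts. With an incomplete diary it is somewhat less.

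It would be wrong to read this as saying that late Week 48 visits in general cause failure. A visit 5 days late leaves 23 or 24 days and is essentially safe. Neither the number of subjects affected nor the direction of any net effect on the odds ratio can be derived from the documents, and the effect is probably small. The case for acting is that the rule decides responder status on the primary endpoint, treats identical diaries differently, and leaves EoS and visit mapping open, so two programmers could score the same subject differently.

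**What to change.** Add to the Week 52 row of Table 2-3: if the Week 52 interval contains fewer than 14 diary days because the Week 48 visit was late, use the 28 days ending the day before the Week 52 visit. Define late by reference to the protocol's own visit window, so that the program needs no judgement. Apply the usual 14-day minimum and proration to the replacement interval, and leave all other intervals unchanged. A broader trigger, such as any gap under 28 days, would redefine the primary month for many in-window subjects who have enough data.

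Use one EoS definition in Table 2-3 and section 5.6, say whether the Week 52 visit day counts, and state whether Table 2-1 mapping governs Table 2-3.

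The cost is a few SAP sentences and a small program change, to be fixed before database lock and without reference to outcomes, since the trial is open-label. The downside is that in these few subjects some diary days also belong to the Week 48 interval and may precede the late Week 48 visit, and hence the last erenumab dose. The overlap does not affect a binary endpoint read at Week 52 alone.
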